The effect of exposure to a range of frequencies from 350 to 4000Hz at a pressure level of 40dB on subjective sleep quality scores, sleep onset latency, sleep architecture (time spent in rapid eye movement (REM) and non-REM (NREM) sleep stage 1, 2, 3), number of arousals from sleep and time of wakefulness after sleep onset in a group of healthy subjects.

III. SUBJECT SELECTION

We will recruit a group of 20 healthy controls aged 21 to 65 years old. Normal controls will be recruited from the community, as well as from our existing database of control subjects, and will be completely healthy and thus without medical or sleep problems.

PARTNERS HUMAN RESEARCH COMMITTEE DETAILED PROTOCOL

Version: March 15, 2016

Exclusion criteria:

- Individual affected by insomnia or other sleep-related diseases.
- Individual taking any medication known to influence sleep/arousal state

Equal number of males and females will be recruited. We will consider all applicants regardless of sex, race, color, creed, or national origin.

IV. SUBJECT ENROLLMENT

Subjects will be recruited through email, telephone, newspaper, and or bulletin advertisements. Only subjects who have stated in the initial clinical questionnaire that they are interested in hearing about research studies will be contacted by phone. Should the subject be interested in the study, they can call the study physician or coordinator to inquire about study participation. We will also recruit from our existing database of research participants.

Subjects who respond will be given a thorough review of the risks, discomforts, potential benefits to the study and their expected involvement using a prepared script approved by our Institutional Review Board. Subjects will be given a copy of the informed consent and allowed a minimum of 24 hours to review the information and make a decision on study participation. During this time, the subject will have the opportunity to discuss the research with his/her primary care physician or clinician. The study investigators will be available to answer any questions should any arise. Informed consent will be obtained from all subjects by the principal investigator or a co-investigator prior to commencement of any study procedures. Subjects will be informed that they may withdraw from the study at any point, with no impact on their ongoing care.

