Inclusion and exclusion criteria will be carefully assessed prior to enrollment. Assuming subjects meet the inclusion criteria, they will begin the protocol by scheduling their overnight studies in the clinical/physiology laboratories. Subjects will be informed that they may withdraw from the study at any point, with no impact on their ongoing care. We have not previously had difficulty enrolling participants into similar studies performed in our laboratory.

V. STUDY PROCEDURES

Protocol:

The protocol will be composed by 2 overnight sleep studies (a night with no noise and a night with background noise) to be conducted at Brigham and Women's Hospital. The 2 nights will be performed approximately one week apart in random order. Sleep will be scored by an expert sleep technologist blinded to the randomization order. Pittsburgh Sleep Quality Index questionnaire will be administered to all study participants before sleep on the first study night. Stanford Sleepiness Scale score and a subjective sleep quality score will be obtained from every subject after each study night.

Measurements and equipment:

Subjects will be instrumented with standard polysomnography (PSG) recording sensors. Sleep stage and arousals will be measured with electrodes pasted on to the scalp, face, chin and chest (EEG, EOG, EKG, chin EMG). Paste-on EMG electrodes will be placed over the anterior tibialis muscle to detect leg

PARTNERS HUMAN RESEARCH COMMITTEE DETAILED PROTOCOL

Version: March 15, 2016

movements. Respiratory effort belts will be placed around the chest and abdomen to measure breathing movements. Oxygen saturation will be measured continuously with a pulse oximetry probe placed on either the fingertip or earlobe. Snoring will be detected with a small microphone positioned over the suprasternal notch. Body position will be recorded with a sensor taped to the thoracic belt. Each of these devices is standard for diagnostic PSG and should not be uncomfortable.

The mixed frequencies noise background will be delivered by four speakers included in two wall mount modules powered by A/C and will include a range of frequencies from 350 to 4000Hz at a pressure level of 40dB (Nightingale, Cambridge Sound Management). The system will be activated at “lights off” time via computer by a co-investigator or a trained student who will monitor patients and data recordings overnight.

Data Analysis:

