Sleep will be scored by an expert sleep technologist blinded to the randomization order following American Academy of Sleep Medicine rules.

If the data collected will be considered insufficient, the subject will be asked to repeat the whole study or a part of it without signing a new informed consent form.

Reimbursement

Subjects will receive \$100/night for participation in each overnight study (TOTAL = \$200).

Reimbursement for parking expenses will be provided.

If the subjects will repeat a part or the entire protocol because of insufficient data collection, they will be reimbursed \$100 for any extra night.

VI. BIOSTATISTICAL ANALYSIS

In this protocol we want to collect pilot data to measure the possible size effect of this intervention. Variables of interest will be compared using a Student T-test with $p<0.05$ considered as statistically significant.

VII. RISKS AND DISCOMFORTS

We believe that the risks associated with participation in this study are minimal. All study procedures have been conducted in our laboratory without serious incident. Anticipated risks and discomforts are listed below:

1. The equipment used for assessing sleep (paste on electrodes) is standard and poses no risk. The electrodes may be mildly uncomfortable and could cause some sleep interruption. Thus subjects may feel somewhat tired the day following this study.
2. The background noise could cause sleep disruption and mild discomfort at wake-to-sleep transition. In case the subject will not tolerate the noise we will reduce the intensity or stop the noisy signal.

PARTNERS HUMAN RESEARCH COMMITTEE DETAILED PROTOCOL

Version: March 15, 2016

VIII. POTENTIAL BENEFITS

Although it is unlikely that there will be any direct physical benefit to the subjects from participating in this study, we will make known to each subject, if requested, some of the information we have gathered from this physiologic testing. This study provides a unique opportunity to gain insight into the specific mechanisms by which continuous background noise may improve sleep quality. The results may, in the future, lead to improved strategies for the treatment of insomnia. However, if previously unknown abnormalities of sleep are encountered, this information will be passed onto the subject. Results can be forwarded to the primary care physician or clinician at the request of the subject.

IX. MONITORING AND QUALITY ASSURANCE

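### The two-night crossover is analysed by an unadjusted t-test, with no night-order term and no stated balance of order, so any difference between night 1 and night 2 costs precision and can shift the noise effect either way

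*Combined protocol and SAP*

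**What the plan says.** Section III sets the sample: "We will recruit a group of 20 healthy controls aged 21 to 65 years old". Section V gives each of them two studies, "a night with no noise and a night with background noise", and states: "The 2 nights will be performed approximately one week apart in random order". Neither section gives an allocation ratio, a blocking rule or a balance of order. The only balance mentioned, in Section III, is between men and women.

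Section VI is the whole statistical plan. Its purpose is stated as "In this protocol we want to collect pilot data to measure the possible size effect of this intervention", and its method as "Variables of interest will be compared using a Student T-test with" a 0.05 significance threshold. It does not say whether the test is paired, and it has no night, period or sequence term.

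Two other statements bear on the point. Section VII says of the sensors: "The electrodes may be mildly uncomfortable and could cause some sleep interruption". Section V, under Data Analysis, allows repeats: "If the data collected will be considered insufficient, the subject will be asked to repeat the whole study or a part of it". It does not say what place a repeated night takes in the order.

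**The concern.** In a two-period crossover the outcome can change between periods for reasons unrelated to treatment. That is plausible here. There is no adaptation night, and the protocol accepts that the electrodes may disturb sleep. It does not say that this disturbance differs between nights, so a night difference is a possibility and not a documented fact.

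If there is one, a simple paired test handles it badly in two ways. Subjects with the noise night second carry the night difference with one sign and the others with the opposite sign, so it spreads the paired differences and inflates their SD. And if one order is commoner than the other, the signs do not cancel and part of the night difference is added to the noise effect.

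Both touch what the pilot is meant to deliver, the size of the effect. The interval is wider than it need be. With balanced order, or on average over orders, the standardised effect is too small; in a single unbalanced sample it can be too large or too small. Omitting the word *paired* is a smaller matter, a gap in wording, since paired is the natural reading.

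**Working it through.** **Inputs from the protocol.** n = 20 (Section III); two nights per subject in random order (Section V); alpha 0.05 (Section VI). The sample size comes with no power, effect size or SD, so there is no stated figure to reproduce.

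**Assumptions, none documented.** Two-sided test; simple (unrestricted) randomisation of order where the text is silent; within-subject correlation ρ = 0.5; night difference π of 0, 0.2, 0.5, 0.8 or 1.0 SD of one night's outcome, with 0.8 to 1.0 as the upper end. At ρ = 0.5 the SD of a paired difference is √(2(1 − 0.5)) = 1 SD of one night, so the two scales coincide.

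**Model.** For subject i, the noise-minus-quiet difference is d_i = τ + s_i·π + e_i, with SD(e) = 1, s_i = +1 if noise is on night 2 and −1 if on night 1.

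**Benchmark effect.** By the noncentral t distribution, a paired test with n = 20 (19 df) has 80% power at τ = 0.660. This is a yardstick chosen here, not a target of the plan.

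**Precision.** At 10:10 the SD of the differences is inflated by √(1 + π²·20/19). At π = 0.5 this is √(1 + 0.25 × 1.0526) = 1.124, so a true standardised effect of 0.660 appears as about 0.588. At π = 1.0 the factor is 1.433 and it appears as about 0.461.

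Power and interval width by simulation (at least 100,000 runs per cell). The adjusted analysis takes the mean of the two order-group means, with 18 df.

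| Night difference π (SD) | 0 | 0.2 | 0.5 | 0.8 | 1.0 |
|---|---|---|---|---|---|
| Power: simple randomisation, no term | 80% | 78% | 71% | 59% | 50% |
| Power: 10:10 order only | 80% | 79% | 72% | 60% | 49% |
| Power: night term only | 77.5% | 77.5% | 77.5% | 77.5% | 77.5% |
| Power: both | 80% | 80% | 80% | 80% | 80% |
| 95% CI half-width, neither change (SD) | 0.46 | 0.47 | 0.52 | 0.59 | 0.66 |
| 95% CI half-width, both (SD) | 0.46 | 0.46 | 0.46 | 0.46 | 0.46 |

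The last four power figures in the first row become 79/73/64/57% at ρ = 0.3 and 78/65/49/39% at ρ = 0.7.

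**Imbalance.** Under Binomial(20, 0.5), exact 10:10 has probability 0.176 and 13:7 or worse has probability 0.263. The noise estimate shifts by π × (difference between the two order counts)/20. At 13:7 that is (13 − 7)/20 = 0.30 of π, or 0.06, 0.15, 0.24 and 0.30 SD at π = 0.2, 0.5, 0.8 and 1.0.

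At 13:7 and π = 0.5 the mean observed standardised effect is 0.76 if the split favours noise and 0.48 if it does not, against 0.69 with no night difference. (The baseline is 0.69 and not 0.66 because mean/SD is biased upward at n = 20.) With the night term it is 0.69 either way.

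**Type I error.** Over simple randomisation it stays at about 5%. At a realised 13:7 split it is about 6.6% at π = 0.5. At 10:10 without the term it is about 2.8% at π = 0.5, which is conservative.

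**The case against.** The strongest reply is that the premise is undocumented. The electrodes are worn on both nights, so a constant disturbance cancels in the paired difference, and Section V describes the devices as standard and not expected to cause discomfort. Nothing in the protocol says that sleep differs between the nights. This stands, and it is why the figures are a range starting at zero. Over the lower part of that range little is lost: the gain from both changes is nil at π = 0 and about 1 point of power at 0.2 SD.

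Second, the protocol does not say that order is unrestricted. If a blocked list exists in practice, the imbalance half of the point disappears. That also stands, but the precision loss remains: 10:10 order without the term gives 72% at 0.5 SD.

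Third, this is a pilot with no power target, so points lost from 80% are measured against a benchmark the authors never set. That is fair for power. It does not apply to interval width or to a shift in the estimate, because measuring the effect is the stated aim.

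Fourth, each subject's order is known, so the term can be fitted later. That recovers most of the loss (about 77.5% against 80% with both), but a term chosen after seeing the data is not prespecified, and balance cannot be restored.

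**Conclusion.** The concern holds, as a matter of efficiency and not of validity. Neither a night term nor a balance of order is stated, and the paired test remains valid on average over the randomisation.

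Its size depends wholly on a night difference the protocol does not quantify. At 0.5 SD, with correlation 0.5 and simple randomisation, the two changes together are worth about 9 points of power and narrow the interval half-width from 0.52 to 0.46 SD. They also remove a shift of 0.15 SD in either direction at a 13:7 split. With no night difference they gain nothing and cost almost nothing. It should be fixed because the remedy is cheap and bears directly on the quantity the pilot is meant to estimate.

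**What to change.** Make two changes together.

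1. In Section V: *Night order will be randomised from a concealed, blocked list so that 10 subjects have the noise night first and 10 the quiet night first.*
2. In Section VI: *For each outcome, within-subject noise-minus-quiet differences will be analysed with adjustment for night order (equivalently, a mixed model with condition and night as fixed effects and subject as a random effect). The difference will be reported with its 95% CI and the within-subject SD.*

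Also state which night number a repeated night takes. The list must be in place before the first subject is randomised.

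**Cost.** No extra subjects or nights. The term uses one degree of freedom (19 to 18), and at 10:10 with no night difference power goes from 80.0% to 79.8%. Near-balance is enough. With imbalance im, the difference between the order counts divided by n, the adjusted variance is multiplied by 1/(1 − im²): 1/(1 − 0.1²) = 1.01 at 9:11 proportions, against 1/(1 − 0.3²) = 1.10 at 13:7.

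**Do not add the term alone.** Without blocking it costs about 2.5 points when the nights do not differ (79.9% to 77.4%) and pays only above about 0.25 SD. At 10:10 it breaks even at about 0.1 SD.

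**Fallback.** If the simple test is kept, block the order and write *paired t-test*. This removes the imbalance shift but recovers almost no power, and the test becomes conservative if the nights differ.
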